Genetic variation is a primary contributor to individual differences in baseline dopamine neurotransmission (Cools & D’Esposito 2011; Frank and Fossella 2011). Individuals with specific alleles in genes coding for high baseline dopamine demonstrate better performance on tasks probing working memory, cognitive control, and social cognition (Diamond et al. 2004; Egan et al. 2001; Meyer-Lindenberg et al. 2005). Genetic variants in baseline dopamine neurotransmission would therefore be expected to modulate performance-enhancing effects of L-DOPA, such that individuals with low endogenous would be expected to have increased performance upon exogenously increasing dopamine neurotransmission; whereas individuals with high endogenous dopamine would be expected to have performance deteriorate from exogenously increasing dopamine neurotransmission. In support of this hypothesis, a recent study found an interaction between L-DOPA administration and endogenous dopamine neurotransmission (as indicated by a polygenic score pooled across COMT, DAT, DRD1-3) on motor learning performance, such that individuals with a combination of alleles coding for higher baseline dopamine demonstrated a weaker learning benefit from L-DOPA, whereas individuals

**PI:** [name].

with a combination of alleles coding for lower baseline dopamine demonstrated a stronger learning benefit from L-DOPA (Pearson-Fuhrhop et al. 2013). These data demonstrate the non-linear relationship between performance and dopamine levels, suggesting that any investigation of potential effects of boosting dopamine neurotransmission as a means of boosting learning needs to account for baseline dopamine neurotransmission.

Overall, the proposed project seeks to demonstrate the engagement of post-extinction dopamine neurotransmission and downstream acute reorganization of dopaminergic resting-state neural networks as a means of increasing consolidation of generic fear extinction learning in adult women with PTSD.

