## **B. Specific Aims**

**Specific Aim 1: Test the degree to which endogenous and exogenous manipulations of dopamine neurotransmission affect fear extinction learning across multiple indices.** *Hypothesis:* L-DOPA dose will interact with dopaminergic gene score to predict fear extinction learning across indices.

**Specific Aim 2: Test the degree to which post-extinction functional connectivity within dopaminergic neural networks mediates the effect of dopaminergic manipulation on fear extinction learning.** *Hypothesis:* The L-DOPA x dopaminergic gene score will predict enhanced post-extinction dopaminergic functional connectivity, which in turn predicts enhanced fear extinction recall.

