**Planned Fear Extinction Analyses:** We would conduct three sets of MANOVA analyses, one with the set of Day 2 neural circuit indices (amygdala, dorsal anterior cingulate cortex, caudate) as dependent variables, one with the set of Day 2 physiological indices (SCR, HR, HRV) as dependent variables, and one with the set of Day 2 verbal/self-report indices (anxiety, UCS expectation) as dependent variables. In these analyses, the mixed effects of L-DOPA group, dopamine gene score, cue, context, and the interactions are entered as factors explaining variance in the multivariate combination of the set of dependent variables. Interactions with context would demonstrate the effect of the manipulations on robustness to context renewal effects. Additionally, any factors that differ between groups, such as Day 1 fear responding, age, or comorbid diagnoses, would also be entered as covariates should the balanced "urn" randomization fail. Given the three sets of tests, FDR correction (Benjamini and Hochberg 1995) would be used to control for alpha inflation. If the multivariate analyses reveal significant between-group differences in our measures of neural, psychophysiological and/or verbal/self-report, they would be followed up with simple effect testing to identify the specific conditions and measures driving the larger multivariate effect. We would additionally test for linear and quadratic contrasts for the group comparisons in order to establish dose-dependent learning, and its gating by dopamine gene score, effects on these primary DVs. All analyses would be completed prior to breaking the blind in order to minimize bias.

*Defining dopaminergic resting-state functional connectivity (FC).* Following the prior studies cited above (Haaker, Gaburro, Sah, Gartmann, Lonsdorf, Meier, Singewald, Pape, Morellini, & Kalisch 2013a; Kelly, de, Di, Copland, Reiss, Klein, Castellanos, Milham, & McMahon 2009), we

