would define three regions-of-interest (ROIs) with which to calculate resting-state FC: 1) the substantia nigra/ventral tegmental area (SN/VTA; MNI X, Y, Z coordinates = -8, -18, -20 mm), a critical region of the dopaminergic midbrain, 2) the dorsal caudate (DC; MNI X,Y,Z coordinates =  $\pm 13, 15, 19$  mm), and the ventral (limbic) striatum (VS; MNI X,Y,Z coordinates =  $\pm 16, 12, -10$  mm). Consistent with our prior RSN FC analyses (Cisler et al. 2012; Cisler et al. 2013), we would characterize FC with these seed regions using the following approach within each individual separately. First, we would extract the first principal component timecourses of 6 mm spheres centered separately on the three ROIs. Second, the seed region timecourse would be regressed onto the timecourse of every other voxel (i.e., whole-brain analyses) using an autoregressive model (AFNIs 3dREMLfit) and using an *r*-to-*z* transformation to improve normality. This would result in a separate whole-brain spatial map, indicating its degree of FC with the seed region, for each ROI and each participant.

*Defining the effect of L-DOPA and dopamine gene score on striatal and mid-brain FC.* Between-group GLMs would analyze functional connectivity (FC) using a 3 (group: placebo vs 100 mg L-DOPA vs 200 mg L-DOPA) x 2 (cue: CS+ vs CS-) x 6 (dopamine gene score: 0 [low endogenous dopamine] – 5 [high endogenous dopamine]) between-subjects ANOVA in a whole-brain, mass univariate, approach. Covariates of non-interest would be included if the “urn” balanced randomization procedure should fail to match groups on demographic and clinical severity variables. Cluster-level thresholding would be used to correct for multiple comparisons. This approach would identify clusters of voxels where FC with the SN/VTA, DC, or VS differed significantly as a function of L-DOPA, dopamine gene score, or the interaction. This analysis establishes the engagement of the intermediate mechanism in the proposed conceptual model hypothesized to mediate dopamine neurotransmission’s pro-extinction effect.

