*Testing the effect of altered resting-state FC on fear extinction learning consolidation.* Following identification of regions where FC with the DC, VS, and SN/VTA differ as a function of the L-DOPA x gene score interaction, we would then test whether individual differences in FC within these clusters predict subsequent consolidation of fear extinction learning. That is, we would test whether the hypothesized intermediate mechanism (acute dopamine neurotransmission and downstream dopaminergic neural networks) is related to the ultimate mechanism of interest (fear extinction learning). Consolidation of fear extinction learning from Day 1 would again be tested using Day 2 fear expression indices in Context A and Context B (i.e., fear extinction learning recall test) using multimodal assessments (neural circuit indices, psychophysiological, and self-report). GLMs would be used in which the outcome variable is regressed simultaneously onto the FC cluster, L-DOPA group, dopamine gene score, cue, and context. This would be repeated for the separate fear expression indices, with FDR controlling for alpha inflation due to multiple comparisons. These analyses would identify the clusters of voxels whose FC with the VS, DC, and SN/VTA predict enhanced recall on Day 2.

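### The listed Aim 2 outcome model has no L-DOPA x gene score, FC x cue or FC x context term, so part of a direct drug-by-gene effect on recall can be credited to FC, and discrimination and renewal go untested where they need those terms

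*Combined protocol and SAP*

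**What the plan says.** All references are to the combined protocol and SAP.

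- B. Specific Aims, Aim 1 hypothesis: "L-DOPA dose will interact with dopaminergic gene score to predict fear extinction learning across indices".
- B. Specific Aims, Aim 2: "Test the degree to which post-extinction functional connectivity within dopaminergic neural networks mediates the effect of dopaminergic manipulation on fear extinction learning". The hypothesis is that the drug-by-gene interaction raises FC, which in turn predicts better recall.
- G. Statistical Plan, Testing the effect of altered resting-state FC: the clusters carried forward are defined by "Following identification of regions where FC with the DC, VS, and SN/VTA differ as a function of the L-DOPA x gene score interaction". The outcome model is then "GLMs would be used in which the outcome variable is regressed simultaneously onto the FC cluster, L-DOPA group, dopamine gene score, cue, and context", repeated for each fear-expression index with FDR control. The paragraph speaks only of FC predicting, or being related to, recall.
- Same section, Planned Fear Extinction Analyses (Aim 1): here "the mixed effects of L-DOPA group, dopamine gene score, cue, context, and the interactions are entered as factors explaining variance", and "Interactions with context would demonstrate the effect of the manipulations on robustness to context renewal effects".
- Same section, Neural circuit ROI definition: the neural indices are extracted as CS+ versus CS- contrasts, separately by context. No such differencing is described for SCR, HR, HRV, anxiety or UCS expectation.

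No section describes estimating an indirect effect.

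**The concern.** Because the clusters are chosen for carrying the drug-by-gene interaction, FC is correlated by design with the product term that the outcome model leaves out. If the interaction also reaches recall by a route other than FC, as Aim 1 leaves open, the FC coefficient absorbs some of it. FC could then be reported as the mechanism although it merely marks the dose-by-gene pattern.

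There is a second problem. Extinction recall is about responding to CS+ relative to CS-, and about whether fear returns in Context A. For an outcome recorded separately for each cue, an FC main effect with cue as an additive factor estimates the effect of FC averaged over CS+ and CS-. General reactivity could be read as better or worse recall, and a genuine effect on discrimination could be missed. For every outcome, an FC main effect also averages over contexts and does not address renewal.

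**Working it through.** **1. The plan's own figure.** Power Analyses and Targeted Sample Size gives 35 per group, N = 105, power above .9 for large and about .8 for medium-large effects. Assuming two-sided alpha .05 and a 2-df test, f = .40 gives .96 and f = .305 gives .79, so the figures reproduce. They are not specific to Aim 2; none is given for this model. The sizes f = .25 and f = .40 below are therefore assumptions.

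**2. Leakage with the product omitted.** Let FC = a·W + e and recall Y = c·V + u. W and V are unit-variance drug-by-gene patterns with correlation r, e and u have SD 1, and FC has no effect on Y. The listed model has 5 coefficients (intercept, two for group, score, FC) per outcome value, so df = 105 − 5 = 100.

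- Spurious FC slope: b = a·c·r/(1 + a²)
- Residual variance: v = 1 + c² − (a·c·r)²/(1 + a²)
- Standard error: √{v/[(1 + a²)·100]}

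Results:

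- a = c = .25, r = 1: b = .0625/1.0625 = .0588; v = 1.0588; SE = √(1.0588/106.25) = .0998; ratio .59; rejection about 9%.
- a = c = .40, r = 1: b = .16/1.16 = .138; v = 1.138; SE = √(1.138/116) = .0990; ratio 1.39; rejection about 28%.
- r = .5: about 6% and 10.5%.
- r = 0: 5%.

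Simulation with a Binomial(5, .5) gene score agrees: 8–10% and 28–29% for r = 1. When FC is linear in dose (−1, 0, 1) and recall is inverted-U in dose (−1, 2, −1), which are orthogonal contrasts, the rate is 4–5%. With no direct effect it is about 5%. With group x score included it is about 5% throughout when the interaction is linear in score.

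The share of the direct effect credited to FC when r = 1 is a·b/c = a²/(1 + a²): 5.9% at .25 and 13.8% at .40.

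**3. Is a linear product enough?** Section A says "These data demonstrate the non-linear relationship between performance and dopamine levels". If the interaction is purely quadratic in score at .40/.40, simulation gives 27–28% omitted, 25–26% with a linear product, and about 5% once score squared and its products with group are added. Over 36 bell-shaped inverted-U curves at .40/.40, the median rates are .284, .066 and .052. The linear product thus removes (.284 − .066)/(.284 − .05) = 93% of the excess at the median, but the worst curve still leaves .222.

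**4. Cue.** Take a non-neural outcome with residual SD 1 per cue and CS+/CS- correlation .5 (assumed).

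- FC acts on CS+ only, by .3 SD. The main effect is .15 with SD √{(1 + .5)/2} = .866, so the ratio is about .15/.0866 = 1.73 and power about .4. The difference is .3 with SD √{2(1 − .5)} = 1, ratio 3.0, power about .85. Over correlations .5 to .8, simulation gives .36–.41 against .85–.995.
- FC shifts both cues by .3 SD. The main effect is significant in 89–92% of runs and FC x cue in about 5%, although discrimination is unchanged.

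If FC x cue is tested but group x score is not crossed with cue, the leakage returns: .088 at .25/.25 and .281 at .40/.40, against about .05 when crossed.

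**5. Context.** This needs no arithmetic. The Aim 1 paragraph makes context interactions the test of renewal, while the Aim 2 list has context only as an additive factor.

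The whole-brain search and the FDR step were not modelled.

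**The case against.** The strongest reply is that a list of variables is not an exclusion. The Aim 2 paragraph says recall is again tested with the Day 2 indices in both contexts, and the framework before it includes interactions. That is fair: the documents never rule the products out, and the authors may intend them. But the Aim 1 paragraph names its interactions and the Aim 2 sentence does not, so an analyst following the text would fit main effects. If they are intended, saying so takes one sentence.

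A reader might infer that every interaction effect bypassing FC is credited to FC. That does not follow. Only the part sharing FC's dose-by-gene pattern leaks, and only a fraction of that part. The 9% and 28% are same-pattern cases.

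A reader might also want score squared in the primary model. The genetic evidence in Section A is directional (weaker benefit with higher-dopamine alleles, stronger with lower), and the linear product removes most of the excess in most inverted-U cases. This supports a sensitivity model.

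Finally, a reader might infer that the plan will declare mediation from this regression. Mediation language appears in Aim 2 and in the FC-definition paragraph, but the outcome paragraph itself claims only prediction and relatedness. It is also true that unmeasured FC-outcome confounding may matter more: with the product terms (linear and quadratic) included, a residual correlation of .1, .2 or .3 makes FC significant in 16%, 51% or 85% of runs. That limits what the fix can achieve; it does not excuse the omission.

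**Conclusion.** The concern holds in a limited form, and the plan should be changed. Followed as listed, the FC test is anti-conservative whenever a direct drug-by-gene effect on recall resembles the one on FC. The size depends on effect sizes that the documents do not give: little when the direct effect is small, about 9% at .25/.25 and 28% at .40/.40 against a nominal 5%, and nothing when the direct effect is absent or orthogonal. These rates assume one outcome, 35 per group, a Binomial(5, .5) score and two-sided alpha .05.

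The cue point applies to SCR, HR, HRV and self-report only, since the neural indices are already contrasts. The missing FC x context term affects all outcomes. The documents support saying that these terms are not listed, not that they are forbidden.

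**What to change.** In the paragraph on testing the effect of altered resting-state FC:

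1. Add group (three-level factor) x gene score to the outcome model. As a sensitivity analysis, add score squared and its products with group.
2. For SCR, HR, HRV and self-report, analyse the CS+ minus CS- difference, or test FC x cue with the group x score terms also crossed with cue. Test FC x context for all outcomes. Account for repeated measures within participant.
3. Keep the existing predictive wording for the Aim 2 conclusion, and do not claim mediation unless an indirect effect is estimated.

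Cost: no new data. Step 1 uses two more model degrees of freedom, and three further ones in the sensitivity model; crossing terms with cue and context uses more. If mediation is complete, power falls slightly. At an FC slope of .30 it goes from about .86 to .83–.84 when f = .25 on FC, and from .89 to .82–.84 when f = .40; the sensitivity model gives about .82–.83. At a slope of .20 with f = .40, the sensitivity model takes power from .56–.58 to .49–.50.

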The fear extinction phase would occur in Context B (with the target stimuli presented against a blue background), during which the CS+ is no longer followed by the UCS. The shapes and background would be counterbalanced as CS+, CS-, Context A, and Context B.

The recall phase occurs ~24 hours later on Day 2, during which participants are presented with the CS+ and CS- alternating between Contexts A and B in a pseudorandom manner, and no presentations of the UCS. The alternation between the contexts allows for testing resistance to context renewal of the fear memory. Every fourth trial, participants also provide self-report ratings of the anxiety elicited from the CS+ and CS- and expectation of the UCS following each CS using a Likert Scale of 0-10. In each phase, there are 12 presentations of the CS+ and CS-.

*Resting task.* The connectivity of the mesolimbic dopaminergic system will be investigated using a standard resting state task, in which participants lie passively in the scanner for 7 minutes and are simply told to let their mind wander freely.

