### Data analysis.

*Primary Analytic Framework for Fear Extinction Effects.* The overall data analysis framework for Aim 1 fear extinction analyses consists of a 3 (group: placebo vs 100 mg L-DOPA vs 200 mg L-DOPA) x 2 (cue: CS+ vs CS-) x 2 (context: A [learning context] vs B [extinction context]) x 6 (dopamine gene score: 0 [low endogenous dopamine] – 5 [high endogenous dopamine]) mixed design focused on Day 2 fear responding. Preliminary analyses would test for any baseline

differences in fear responding or extinction learning on Day 1 and include these variables as covariates if needed. Analyses would also control for ancestry as well as other demographic or clinical variables should they differ between groups.

*Neural circuit ROI definition and extraction.* The neural circuit indices would be 6 *a priori* regions of interest (ROI) with anatomical coordinates defined from the recent literature (Delgado et al. 2008; Haaker, Gaburro, Sah, Gartmann, Lonsdorf, Meier, Singewald, Pape, Morellini, & Kalisch 2013a; Milad, Wright, Orr, Pitman, Quirk, & Rauch 2007; Phelps, Delgado, Nearing, & LeDoux 2004; Schiller et al. 2008) and include bilateral amygdala, bilateral hippocampus, ventromedial PFC, dorsal anterior cingulate cortex. Following standard preprocessing, first-level analyses conducted for each individual separately would consist of whole-brain GLMs, in which the task design (CS+ vs CS- during Context A vs B) is modeled as boxcar events convolved with a canonical HRF. The task design is regressed onto each voxel's timecourse within a GLM framework and using restricted maximum likelihood to account for serial correlation, resulting in a whole-brain spatial map indicating the degree to which each voxel responds to CS+ vs CS- during Context A vs B. The mean contrast values for CS+ vs CS- as a function of context is then extracted from the voxels within 6 mm spherical ROIs for the six ROIs. These analyses would provide six (for each ROI) indices of activation, calculated separately for each participant, that would be used in multivariate analysis of variance (MANOVA) analyses to define the impact of L-DOPA and dopamine gene score on consolidation of fear extinction learning.

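### The Aim 2 outcome GLM enters FC only as a main effect, so for indices kept by cue it tests overall reactivity rather than conditioned fear, and its participant-level error structure is not stated

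*Combined protocol and SAP*

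**What the plan says.** The last analysis in section G (testing the effect of altered resting-state FC on extinction consolidation) sets out to "test whether individual differences in FC within these clusters predict subsequent consolidation of fear extinction learning". Its model is one sentence. It says that "GLMs would be used in which the outcome variable is regressed simultaneously" on five terms; in full, the outcome is "regressed simultaneously onto the FC cluster, L-DOPA group, dopamine gene score, cue, and context". It names no interaction, participant effect, repeated-measures structure or covariance. The model is repeated for each fear index, with FDR across indices.

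Three other places bear on it:

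- **Level of FC.** The FC definition yields a connectivity map "for each ROI and each participant", so FC is a between-woman variable. Cue and context vary within a woman.
- **Aim 1, for contrast.** The Primary Analytic Framework calls Aim 1 a "mixed design focused on Day 2 fear responding", and the Planned Fear Extinction Analyses state that "the mixed effects of L-DOPA group, dopamine gene score, cue, context, and the interactions are entered as factors".
- **Form of the outcomes.** The task description under MRI Procedures collects "self-report ratings of the anxiety elicited from the CS+ and CS"-, and UCS expectation for each cue, so self-report is kept by cue. The neural index is different: "The mean contrast values for CS+ vs CS- as a function of context is then extracted from the voxels" in each ROI, which leaves two values per woman per ROI, one per context, with cue already differenced out.

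**The concern.** Extinction recall in this task is a differential quantity: the response to CS+ relative to CS-, and how that difference changes between contexts. Where an index is kept by cue, a model with FC as a main effect and cue as a separate main effect gives FC a single slope common to both cues. That slope is about how strongly a woman responds to everything.

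Two errors can follow. A cluster whose FC tracks general reactivity could be reported as predicting extinction recall. A cluster whose FC tracks only the CS+/CS- difference, which is the Aim 2 hypothesis, could be missed. Renewal is not tested at all, because FC has no interaction involving context.

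A second, conditional issue is the error term. A model with all five predictors needs several rows per woman. If those rows were fitted as independent, the standard error of the FC main effect would be too small. FDR does not repair p-values that are already too small.

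**Working it through.** **The plan's own figure.** None is given for this model. The only sizing statement is power above .9 for large and about .8 for medium-large effects with 35 per group. At an assumed two-sided alpha of .05, a three-group ANOVA with N = 105 gives .960 at f = 0.40 and .807 at f = 0.31, so that statement is consistent with conventional values. It does not bear on this point.

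**Inputs.** N = 105 in three groups of 35 (Power Analyses). Rows per woman, m: 4 for an index kept by cue and context, 2 for the neural contrast by context. The within-woman correlation rho is not in the documents; .1 to .7 is an assumed range.

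**Step 1: what the FC coefficient targets.** Write Y = b0 + b1·FC + b2·cue + b3·context + group and gene-score terms, with cue coded +.5 for CS+ and -.5 for CS-. The FC slope is b1 for both cues, so the modelled effect of FC on CS+ minus CS- is b1 - b1 = 0 by construction. Adding b4·FC·cue makes that effect b4.

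In a simulation (N = 105, four cells per woman, 2,000 runs), FC changed only the difference, by an illustrative 0.3 SD per SD of FC:

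| Test | rho .3 | rho .5 |
|---|---|---|
| FC main effect, one mean per woman (valid error) | .054 | .053 |
| FC on each woman's CS+ minus CS- difference | .936 | .981 |

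The valid main-effect test has no power for that effect. As a check, slope/SE for the difference test is about 0.3 x sqrt(105)/sqrt(1 - rho), which is 3.67 and 4.35.

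**Step 2: error of the FC main effect if rows are treated as independent.** Design effect D = 1 + (m - 1)·rho; reported SE / true SE = 1/sqrt(D); type I error = 2·[1 - Φ(1.96/sqrt(D))].

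| rho | D, m = 4 | SE ratio | Type I | Simulated (3,000 null runs) | D, m = 2 | Type I, m = 2 |
|---|---|---|---|---|---|---|
| .1 | 1.3 | .88 | .086 | .084 | 1.1 | .062 |
| .3 | 1.9 | .73 | .155 | .160 | 1.3 | .086 |
| .5 | 2.5 | .63 | .215 | .214 | 1.5 | .110 |
| .7 | 3.1 | .57 | .266 | .278 | 1.7 | .133 |

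Analysed at participant level, the same null data gave .049 to .059 for the main effect and .045 to .057 for the difference.

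**Step 3: error of FC x cue under the same independent-error fit.** The ratio of true to reported variance is 1 - rho, so the error goes the other way. Simulated type I error was .040, .019, .007 and .001 at rho .1, .3, .5 and .7. Adding FC x cue without a participant term would therefore make that test conservative.

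**Step 4: which participant structure protects FC x cue.** Let women differ in cue response with SD s, relative to residual SD 1.

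- Random intercept only: the variance ratio is (1 + s²)/(1 + s²/3), which is 1.15, 1.32 and 1.50 at s = 0.5, 0.75 and 1.0. Type I error is about .068, .088 and .110 (simulated .064, .085, .115).
- CS+ minus CS- difference with two rows per woman and no participant term: the ratio is 1 + s²/(s² + 2), which is 1.11, 1.22 and 1.33. Type I error is about .063, .076 and .090 (simulated .059, .075, .094).
- One context-averaged difference per woman: about .05 throughout.

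**The case against.** The strongest reply is that the plan never says rows are independent. GLM can mean a repeated-measures GLM, which tests FC against between-woman error. The first-level imaging GLM in the same section does handle serial correlation, and the Aim 2 text returns to the same Day 2 indices that Aim 1 analyses as a mixed design. This stands. A reader might infer that the plan enters four separate observations per woman and so understates its error. The documents do not support that reading: they leave the error structure unstated. Nor do they settle the matter the other way, because the mixed-design language is written for Aim 1 only, and the preceding FC analysis places cue in an ANOVA labelled between-subjects.

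A reader might also infer that Aim 2 fails to target conditioned fear for every outcome. That is wrong for the neural indices. They are already CS+ versus CS- contrasts by context, so an FC main effect on them does address differential response, with two rows per woman at most. What remains there is an inconsistency: cue is listed as a predictor of an index from which cue has been differenced out.

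Finally, it would be too strong to say that a corrected error term makes reported p-values less favourable in general. Step 3 shows the opposite direction for FC x cue.

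None of this touches the missing interaction. Whatever error structure is used, a common FC slope across cues cannot describe the CS+/CS- difference.

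**Conclusion.** The concern holds in a limited form. For indices kept by cue (anxiety, UCS expectation, and SCR and heart rate if scored by cue), the model as listed tests overall reactivity, not differential conditioned fear or renewal. Followed literally, it would not answer the Aim 2 question for those indices. This rests on the text alone; the power contrast of about .05 against .94 to .98 is illustrative and depends on the assumed slope.

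The error-term finding is that the structure is unspecified. Inflation to .155, .215 and .266 (four rows) or .086, .110 and .133 (two rows) at rho .3, .5 and .7 applies only to the FC main effect, only under an independent-error fit, and only for the assumed correlations. The point should be corrected before analysis; it needs no change to the data collected.

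**What to change.** For indices kept by cue, name FC x cue as the tested term for extinction recall and FC x cue x context as the tested term for renewal. Use either of these, keeping group and gene score in the model:

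- a mixed model with a by-woman intercept and a by-woman cue slope; or
- just as simply, two regressions with one row per woman: the context-averaged CS+ minus CS- difference on FC (for FC x cue), and the Context A minus Context B change in that difference on FC (for FC x cue x context).

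A random intercept alone, or a difference regression with two rows per woman and no participant term, is not enough if women differ in cue response (step 4).

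For the neural contrasts, drop cue from the predictors so that the model agrees with the ROI extraction text, and include a participant term across the two contexts. State whether SCR, HR and HRV are scored by cue, so that it is clear which form applies.

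The cost is analysis code and a sentence or two in section G. FC main-effect p-values may become less favourable; FC x cue p-values need not.
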